The qualitative variables analysed were: gender, body mass index (BMI) by rank, sock type, dermal lesions (all lesions developed during the hike, both keratopathies with keratinisation disorder and dermatopathies without keratinisation disorder), muscle lesions (all lesions developed during the hike) and nail lesions (all nail lesions developed during the hike, both traumatic and non-traumatic onychopathies). The height and weight data obtained were used to calculate BMI by rank, interpreted according to the World Health Organization classification [41] (Table 2).

Table 2. Qualitative variables and categories. BMI= Body mass index.

Qualitative variable	Category	
Gender	Male Female	
BMI	Underweight (<18.5) Normal weight (18.5-24.99) Overweight (25.0-29.9) Obese ((>30)
Sock type	Technical (Tierra) Technical (Set) Non-technical (Cotton)	
Skin lesion	Blister Injury (Erosion & chafing) Reddened skin Urticaria Crevice H	Ieloma
Muscle lesion	Pain due inadequate warm Inflammation Muscle discomfort Sprain	
Nail lesion	Onychocryptosis Subungueal hematoma	

The quantitative variables analysed were: age, body mass index (BMI), temperature of each foot measured in two aspects (plantar and dorsal), and perimeter of each foot, measured in four areas (dorsal aspect of toes, instep, heel, tibia).

5. Measuring instruments

The height range and the pace hikers was controlled with a Garmin ETREX 20X GPS (Global Positioning System). Perimeter was measured with a flexible, non-elastic tape measure (Lawton 18-0160, precision 1 mm). Weight was measured using scales (Tanita UM-076, precision 0.1kg) and height was measured using the weight rod of different scales (SECA 704, precision 1 mm).

Temperatures were taken with an infrared thermometer (FTN Medisana, precision 0.18° C), calculating the mean of the three measurements. An intra rate of the measure was done to detect the error of the measure of the temperature, obtaining an error of 0.1452.

6. Statistical tests

The data were analysed using IBM SPSS Statistics for Windows, Version 22.0 (IBM, Armonk, New York). The statistical treatment consisted of data study and cleansing, descriptive variable analysis, normality test (Shapiro-Wilks test). The studies of normality were no significant (p-values between 0.000 y 0.044).

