Quantitative variables depending on whether the samples were paired or independent, Friedman's test for related samples and Kruskal-Wallis was performed for independent samples, both with Bonferroni correction for multiple testing was applied. For the qualitative variables the

chi-square or Fisher's exact test with a significance level of α = 0.05 was carried out. The variables analysed by logistic regression were quantified using the ODDS Ratio (OR). The effect size for the different variables was also calculated. First, for Kruskall-Wallis tests, the variation was between 0.443 y 0.888, and for Friedman tests, the variation was between 0.336 y 0.623. Therefore, in both cases the effect size could be considered median and high.

All p-values = 0.000 are less than 1 per 1000.

Results

After completing the first part of the hike, the most frequent dermal lesions among participants were blisters and erosions.

Table 3. Prevalence of skin, muscle and nail lesions during the 0-14.5 km of the hike by sex.

(0.14 = 1)				Fen	nale					Ma	ıle		
(0-14.5 km)		Tier	ra %	Se	et %	Cott	on %	Tier	ra %	Set	%	Cott	on %
Skin lesion	%Tt.	RF	LF	RF	LF	RF	LF	RF	LF	RF	LF	RF	LF
Blister	12.8	0.0	4.0	8.0	7.7	22.2	27.8	0.0	5.3	5.3	0.0	6.7	13.3
Erosion	2.8	0.0	0.0	0.0	0.0	11.1	5.6	0.0	0.0	0.0	0.0	6.7	0.0
(0.44.5.1)				Fer	male					Ma	ıle		
(0-14.5 km)		Tier	ra %	Se	et %	Cott	on %	Tier	ra %	Set	%	Cott	on %
Muscle lesion	%Tt.	RF	LF	RF	LF	RF	LF	RF	LF	RF	LF	RF	LF
Pain due inadequate warm	21.1	23.1	27.8	8.0	7.7	27.8	27.8	10.5	15.8	10.5	0.0	13.3	13.3
Inflammation	2.8	0.0	4.2	4.0	0.0	0.0	0.0	0.0	10.5	10.5	0.0	0.0	0.0
Muscle discomfort	1.8	0.0	0.0	0.0	0.00	0.0	0.0	5.3	5.3	0.0	0.0	0.0	0.0

Km=Kilometres, %=Percentage, Tt=Total, RF=Right foot, LF=Left foot.

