The differences in temperature are greater at the beginning of the hike than at the end. An increase in temperature from 0 km to 14.5 km was observed, and temperature stabilization of 14.5 km to 29.6 km in all types of socks. However, the increase in temperature, from the beginning to the end of the hike, varies between the types of socks in all the areas measured at the foot of the walkers; being superior when using non-technical socks (about 8.5°C) than in the case of using technical socks (about 1.2°C) (Supplementary data, tables A, B).

Table 5. Women's foot temperature by sock type.

					FEMAL	E			
Distance	Sock P-value sock			P-	value distanc	e			
(km)	Т	S	С	T-S	T-C	S-C	T	S	С
				Dor	sal temp (°C) RF			
0	34.7	35.0	19.9	1.000	0.000*	0.000*	(1)=0.002*	(1)=0.000*	(1)=0.001*
14.5	36.2	36.3	31.8	1.000	0.013*	0.000*	(2)=0.000*	(2)=0.000*	(2)=0.000*
29.6	36.3	36.3	30.6	1.000	0.000*	0.000*	(3)=1.000	(3)=1.000	(3)=0.867
				Dor	sal temp (°C) LF			
0	35.0	35.0	19.9	1.000	0.000*	0.000*	(1)=0.000*	(1)=0.005*	(1)=0.003*

14.5	36.4	36.2	32.2	0.931	0.002*	0.036*	(2)=0.000*	(2)=0.001*	(2)=0.000*
29.6	36.3	36.3	30.8	1.000	0.000*	0.000*	(3)=1.000	(3)=1.000	(3)=0.472
				Plan	tar temp ((ºC) RF			
0	34.8	34.8	20.5	1.000	0.000*	0.000*	(1)=0.007*	(1)=0.000*	(1)=0.000*
14.5	36.0	36.2	29.7	1.000	0.000*	0.000*	(2)=0.001*	(2)=0.000*	(2)=0.000*
29.6	36.2	36.2	30.6	1.000	0.000*	0.000*	(3)=1.000	(3)=1.000	(3)=1.000
				Plan	tar temp	(ºC) LF			
0	34.8	34.9	21.0	1.000	0.000*	0.000*	(1)=0.002*	(1)=0.009*	(1)=0.000*
14.5	36.2	36.0	30.2	0.287	0.000*	0.000*	(2)=0.000*	(2)=0.000*	(2)=0.000*
29.6	36.1	36.0	30.2	1.000	0.000*	0.000*	(3)=0.420	(3)=0.785	(3)=1.000

Km=Kilometres, T=Tierra, S=Set, C=Cotton, Temp=Temperature, (°C)=Degrees centigrade, RF=Right foot, LF=Left foot, (*)=Significant difference, (1)= Distance between 0-14.5 Km, (2)= Distance between 0-29.6 Km, (3)= Distance between 14.5-29.6 Km.

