By gender, no significant differences were detected between technical socks models nor in women (p-values> 0.287) nor in men (p-values> 0.249). However, significant differences were detected between each model of technical socks and the non-technical sock for all distances and areas of the feet measured (Tierra-Cotton p-values<0.013 in women and p-value<0.036 in men) and (Set-Cotton p-values<0.036 in women and p-value<0.014 in men). Regarding the distance in both men and women, differences were observed from the beginning to the end and from the beginning to the middle route with all the models. In addition, in the case of men the tendency is observed in the plant of both feet to increase the temperature from the middle to the end of the hike (LF p-value=0.056, RF p-value=0.091) although it cannot be considered statistical significance (tables 5 and 6).

Table 6. Men's foot temperature by sock type.

					MAL	.E			
Distanc		Sock		P	-value sock]	P-value dista	nce
e (km)	T	S	С	T-S	T-C	S-C	Т	S	С
]	Dorsal temp	(°C) RF			
0	34.	35.1	22.0	1.000	0.000*	0.000*	(1)=0.005	(1)=0.017	(1)=0.003*
	9						*	*	
14.5	35.	36.1	32.9	1.000	0.030*	0.014*	(2)=0.000	(2)=0.000	(2)=0.000*
	9						*	*	
29.6	36.	36.4	30.0	1.000	0.000*	0.000*	(3)=0.470	(3)=0.223	(3)=0.896
	3								
]	Dorsal tem	p (ºC) LF			
0	35.	35.3	21.4	1.000	0.000*	0.000*	(1)=0.008	(1)=0.240	(1)=0.003*
	2						*		
14.5	36.	36.0	32.5	0.931	0.036*	0.002*	(2)=0.000	(2)=0.003	(2)=0.000*
	3						*	*	
29.6	36.	36.4	30.8	1.000	0.000*	0.000*	(3)=0.128	(3)=0.401	(3)=0.558
	5								
				I	Plantar tem	p (ºC) RF			
0	34.	35.1	22.0	1.000	0.000*	0.000*	(1)=0.011	(1)=0.017	(1)=0.004*
	9						*	*	
14.5	35.	36.4	30.3	0.249	0.007*	0.000*	(2)=0.000	(2)=0.000	(2)=0.001*
	8						*	*	
29.6	36.	36.4	29.0	1.000	0.000*	0.000*	(3)=0.091	(3)=0.223	(3)=1.000
	2								
				I	Plantar tem	p (ºC) LF			
0	35.	34.9	21.8	1.000	0.000*	0.000*	(1)=0.006	(1)=0.001	(1)=0.042*
	0						*	*	

14.5	36. 1	35.7	31.2	0.287	0.000*	0.000*	(2)=0.000	(2)=0.000	(2)=0.000*
29.6	36.	36.2	29.3	1.000	0.000*	0.000*	(3)=0.056	(3)=0.401	(3)=0.558

Km=Kilometres, T=Tierra, S=Set, C=Cotton, Dif.=Difference Temp=Temperature, (${}^{\circ}$ C)=Degrees centigrade, RF=Right foot, LF=Left foot, (*)=Significant difference, (1)= Distance between 0-14.5 Km, (2)= Distance between 0-29.6 Km, (3)= Distance between 14.5-29.6 Km.

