Dorsal	hell
Temperature LF: (Three different measures)	
Plantar	
Dorsal	
	toes instep Perimeters LF: (Three different measures)
LESIONS (0-14.5KM)	27.0 1 1 1 1
SKIN LESIONS (SPECIFY RF AND LF)	tibia
Hyperkeratosis Heloma	
BlisterErosion Reeddned skin	hell
UrticariaGrevice Others	
MUSCLE LESIONS (SPECIFY RF AND LF)	
Pain due inadequate warmInflamation	
Muscle discomfortSprain Others	toes instep
NATI LECIONIC (CDECIEV DE ANID LE)	toes
NAIL LESIONS (SPECIFY RF AND LF)	
Onichocryptosissubungual hematoma Others	
Others	
EVED A DETAIL C	
EXTRA DETAILS	

SECOND PART OF THE HIKE (14.5-29.6 Km)	
Temperature RF: (Three different measures)	Perimeters RF: (Three different measures)
Plantar Dorsal	tibia
Temperature LF: (Three different measures)	hell
Plantar	
Dorsal	
LESIONS (14.5-29.6 Km) SKIN LESIONS (SPECIFY RF AND LF)	toes instep
HyperkeratosisBlisterErosionReeddned skin	
Urticaria	
GreviceOthers	
	Perimeters LF: (Three different measures)
MUSCLE LESIONS (SPECIFY RF AND LF) Pain due inadequate warm	tibia
Muscle discomfort Sprain Others NAIL LESIONS (SPECIFY RF AND LF)	hell
Onichocryptosissubungual hematoma Others	
	toes instep
EXTRA DETAILS	
EXTRAGETMENT	

 $\label{thm:continuous} \textbf{Table A.} \ \textbf{Foot temperature by sock type (technical/non-technical)}.$

Distance	Socks		P-value socks	P-value distance	e
(km)	T	NT	T-NT	Т	NT
			Dorsal temp (°C) R	F	
0	35.0	20.7	0.000*	(1)=0.000*	(1)=0.000*
14.5	36.2	32.3	0.000*	(2)=0.000*	(2)=0.000*
29.6	36.3	30.4	0.000*	(3)=0.101	(3)=0.413
			Dorsal temp (°C) L	F	
0	35.2	20.6	0.000*	(1)=0.000*	(1)=0.000*
14.5	36.2	32.4	0.000*	(2)=0.000*	(2)=0.000*
29.6	36.4	30.8	0.000*	(3)=0.101	(3)=0.053
			Plantar temp (°C)	RF	
0	34.9	21.2	0.000*	(1)=0.000*	(1)=0.000*
14.5	36.0	30.0	0.000*	(2)=0.000*	(2)=0.000*
29.6	36.2	29.8	0.000*	(3)=0.091	(3)=0.847
			Plantar temp (ºC) I	F	
0	34.9	21.3	0.000*	(1)=0.000*	(1)=0.000*
14.5	36.0	30.6	0.000*	(2)=0.000*	(2)=0.000*
29.6	36.2	29.8	0.000*	(3)=0.340	(3)=0.736

T=Technical, NT=Non-Technical, Km=Kilometres, Temp=Temperature, (°C)=Degrees centigrade (*)=Significant difference, RF=Right foot, LF=Left foot, (1)= Distance between 0-14.5 Km, (2)=Distance between 0-29.6 Km, (3)= between 14.5-29.6 Km.

Table B. Foot temperature by sock composition.

Distance (km)	Sock			P-value		P-value distance			
	T	S	С	T-S	T-C	S-C	T	S	С
				Dor	sal temp (°C) RF			
0	34.9	35.1	21.2	1.000	0.000*	0.000*	(1)=0.000*	(1)=0.000*	(1)=0.000*
14.5	36.1	36.2	32.3	1.000	0.000*	0.000*	(2)=0.000*	(2)=0.000*	(2)=0.000*

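### Holm step-down would give the temperature comparisons the same family-wise protection as Bonferroni with more power; it moves a few technical-sock p-values below 0.05 but does not overturn the description of approximate stabilisation

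*Combined protocol and SAP*

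**What the plan says.** Section 6 (Statistical tests) names Friedman's test for related samples and Kruskal-Wallis for independent samples, and adds that "both with Bonferroni correction for multiple testing was applied". It does not write out the multiplier or the family of comparisons. The only alpha it gives is attached to the chi-square and Fisher tests for qualitative variables ("with a significance level of α = 0.05 was carried out"). It also explains that "All p-values = 0.000 are less than 1 per 1000".

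The footnote to Table A sets out three comparisons over distance: "1)= Distance between 0-14.5 Km, (2)=Distance between 0-29.6 Km, (3)= between 14.5-29.6 Km". Tables 5, 6 and B use the same three. Tables 5, 6 and B also have three pairwise sock comparisons at each distance (Tierra-Set, Tierra-Cotton, Set-Cotton).

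Two statements in the Results draw on the second-half comparison. The general temperature text reports "temperature stabilization of 14.5 km to 29.6 km in all types of socks". The text by gender describes a rising tendency on men's soles, with "LF p-value=0.056, RF p-value=0.091) although it cannot be considered statistical significance".

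**The concern.** Bonferroni is valid, but with three comparisons it is never more powerful than Holm and often less so, at the same family-wise error. Here the loss falls mainly on one comparison. Temperature rises sharply from km 0 in most blocks, so the two contrasts with km 0 are usually rejected with ease. Holm would then test 14.5 against 29.6 km at 0.05, whereas Bonferroni still demands an unadjusted p below 0.05/3 = 0.0167.

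At stake is the wording on the second half of the hike: whether stabilisation can be asserted for every sock, and whether the men's plantar rise is rightly dismissed as not significant.

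**Working it through.** **Inputs.** Printed pairwise p-values from Tables 5, 6, A and B; three comparisons per block; p = 0.000 read as below 0.001. An alpha of 0.05 is assumed for temperature, because Table 6 stars 0.042 and does not star 0.056.

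**Step 1: are the printed values three times the unadjusted p?** For a Friedman pairwise rank test with three time points, z = d/√(2n), where d is the difference in rank sums, and the Bonferroni value is min(1, 3 × two-sided p). The sample sizes n are inferred; they are close to the group sizes in Table 1, less some missing hikers.

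| 14.5 vs 29.6 km | n | d | z | unadjusted p | × 3 | printed |
|---|---|---|---|---|---|---|
| Table A technical, dorsal RF and LF | 72 | 25.5 | 2.125 | 0.0336 | 0.1008 | 0.101 |
| Table A technical, plantar RF | 72 | 26 | 2.167 | 0.0303 | 0.0908 | 0.091 |
| Table A technical, plantar LF | 72 | 19 | 1.583 | 0.1133 | 0.340 | 0.340 |
| Men's Tierra, plantar LF | 19 | 14.5 | 2.352 | 0.0187 | 0.056 | 0.056 |
| Men's Tierra, plantar RF | 18 | 13 | 2.167 | 0.0303 | 0.0908 | 0.091 |
| Men's Tierra, dorsal LF | 19 | 12.5 | 2.028 | 0.0426 | 0.1278 | 0.128 |

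The tables also agree with one another for the dorsal sites. In Table B, dorsal RF, Tierra (n = 30, d = 10.5) gives 0.526 and Set (n = 42, d = 15) gives 0.305. Together they make n = 72, d = 25.5, which is Table A's 0.101. Dorsal LF works in the same way (14.5 + 11 = 25.5).

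The × 3 does not appear to hold everywhere. For cotton, Table A prints dorsal LF 0.053 and plantar RF 0.847, while Table B prints 0.158 and 1.000 for the same wearers. Since 3 × 0.053 = 0.159, which matches 0.158 within rounding, and 3 × 0.847 exceeds 1, these two Table A cells look unadjusted. None of the results below uses them.

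**Step 2: Holm.** Sort the unadjusted p-values, multiply them by 3, 2 and 1, and keep the running maximum. In Table A, technical, both km-0 contrasts are below 0.001. In the three men's Tierra blocks above, the larger km-0 value is at most 0.011, so its unadjusted p is 0.0037 and its Holm value 0.007. Both km-0 contrasts are therefore rejected, and the third comparison takes printed p / 3.

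| 14.5 vs 29.6 km | Bonferroni | Holm |
|---|---|---|
| Technical, dorsal RF | 0.101 | 0.034 |
| Technical, dorsal LF | 0.101 | 0.034 |
| Technical, plantar RF | 0.091 | 0.030 (provisional) |
| Technical, plantar LF | 0.340 | 0.113 |
| Men's Tierra, plantar LF | 0.056 | 0.019 |
| Men's Tierra, plantar RF | 0.091 | 0.030 |
| Men's Tierra, dorsal LF | 0.128 | 0.043 |
| Men's Tierra, dorsal RF | 0.470 | 0.157 |

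A simulation at n = 18, 19 and 72 gave Holm a family-wise error of at most 0.048 on these rank tests.

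**Step 3: cells that do not change.** Holm cannot give less than printed p / 3 for a Bonferroni value. The smallest such figures for 14.5 vs 29.6 km are:
- Table B: Tierra 0.341/3 = 0.114; Set 0.184/3 = 0.061; cotton 0.158/3 = 0.053.
- Table 5, women's technical socks: six values are capped at 1.000; the others give 0.420/3 = 0.140 and 0.785/3 = 0.262.
- Table 6, men's Set: 0.223/3 = 0.074.

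**Step 4: why plantar RF is provisional.** Table B prints 0.826 for both Tierra and Set at this site. Set's value is attainable (n = 42, d = 10). Tierra's is not at n = 30: d = 8.5 gives 0.818 and d = 8 gives 0.905. If Tierra's d were about 8.5, the pooled d would be 18.5, giving 0.37 with Bonferroni and 0.123 with Holm, and only two of the four technical sites would change. If instead Table A and the Set value are right, Tierra's d would be 26 − 10 = 16, giving 0.117 with Bonferroni and 0.039 with Holm. The tables cannot both stand as printed.

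**Step 5: size.** In Table A the technical-sock rises from 14.5 to 29.6 km are 0.1, 0.2, 0.2 and 0.2 °C, against 1.0 to 1.2 °C in the first half. Section 5 gives a thermometer precision of 0.18 °C and, for measurement error, "obtaining an error of 0.1452".

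**Step 6: correction across sites.** Over the four sites, the smallest Holm value is 0.0303 × 4 = 0.12 for pooled technical socks and 0.019 × 4 = 0.075 for men's Tierra.

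**The case against.** The best defence is that Bonferroni is valid and was the stated method. Changing to a more powerful one after seeing which cells would cross 0.05 is post hoc. That stands, and it is why the Holm values belong beside the Bonferroni values and not in their place.

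It can also be said that stabilisation is a statement about size and does not depend on the multiplier. That stands too: the pooled changes are near measurement error, and no second-half cell changes side in the table that separates the three socks. The men's Tierra feet are part of the pooled technical group, so the two sets of changed cells are not independent evidence. Error is controlled only within a block, and neither set survives correction across its four sites.

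A reader might also infer that Holm reveals a Tierra-Set difference, since plantar LF at 14.5 km in Table B goes from 0.105 to 0.035. The documents do not support a sock effect. Each technical-sock wearer had one sock of each model. On the left foot Tierra is warmer (36.2 against 35.8), while on the right Set is warmer (36.1 against 35.7). By Table 1's counts (44 and 32), left Tierra and right Set belong to the same hikers, so the pattern looks like a difference between hikers.

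What the defence does not remove is that, with the same three comparisons, alpha and error control, a method with no real cost would give different results in several printed cells.

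**Conclusion.** The point holds as one of efficiency and reporting. Holm within each set of three would have kept the family-wise error and brought the second-half comparison below 0.05 at two technical-sock sites (three if Table A's plantar RF is right) and at three men's Tierra sites.

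A reader might go further and conclude that Holm reverses the stabilisation finding, or establishes a material second-half rise with technical socks. The documents support neither. The pooled rises are 0.1 to 0.2 °C, and no printed 14.5 to 29.6 km cell changes side in Table B, in women's technical socks or in men's Set. The men's plantar RF rise with Tierra is larger (35.8 to 36.2, or 0.4 °C), but it belongs to one sock in one sex. Nor can it be said that every printed value was multiplied by 3.

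The conclusion assumes that the cells used are three times the unadjusted p (inferred, with inferred n) and that alpha for temperature is 0.05.

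**What to change.** 1. In section 6, name Holm step-down within each set of three pairwise comparisons, and state the family and the alpha for the temperature tests.
2. Reconcile Tables A and B from the source output (cotton dorsal LF and plantar RF; technical-sock plantar RF), and apply the correction consistently.
3. In Tables 5, 6, A and B, print Holm-adjusted values beside the Bonferroni values, labelled as post hoc because results were already known.
4. In the general temperature text, say that any second-half change with technical socks was small (0.1 to 0.2 °C, near measurement error).
5. In the text by gender, say that the men's Tierra plantar rise is below 0.05 under Holm within its block, but not after correction across the four sites (0.019 × 4 = 0.075).

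The cost is a few sentences and a recalculation from existing unadjusted pairwise values; no new data are needed. Holm offers no simple simultaneous confidence intervals, but none are reported. The downside is that the Holm results are post hoc and control error only within each block.

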To carry out the study, the hiker was previously registered. The researchers contacted the participants to explain the study. In addition, data on age, sex, foot number and associated diseases that prevented the completion of the route were obtained. One hour before starting the route, researchers who did not intervene in the exploration process, made registration and delivery to each hiker of two technical socks (1 Set and 1 Tierra) appropriate to the size of the foot and randomly for the right foot (RF) and left foot (LF). Likewise, it proceeded for non-technical socks (cotton), but in this case both feet wore the same type of sock. All the participants before the initial exploration had their socks put on for half an hour. The hike was low-difficulty, over a short distance [37]. The first 14.5 km were on asphalt and the last 15.1 km on dirt. The height range was 189 m and the pace was moderate, at 5 km/hour. The sample comprised 109 participants (53 men and 56 women). Two women had to give up the hike for personal reasons. Both wore technical socks.

The Table 1 explain the anthropometric characteristics of the participants and the distribution of the socks, differentiating by sex and feet.

Anthropometric variable	Total	Male	Female	
Gender		48.6%	51.4%	
Age (years)	44± 25	49± 21	36 ± 24	
Height (meters)	1.7± 0.1	1.7± 0.1	1.6± 0.1	

81.0±13.5

61.4±7.8

68.8±19.4

Table 1. Anthropometric variables, total sock distribution and sock distribution by gender.

BM	II	24.9± 3.6	26.6± 3.7	23.5± 9.1
Sock type di	istribution	Total %	Male %	Female %
LF sock	Tierra	40.4 (n=44)	35.8 (n=19)	44.6 (n=25)
	Set	29.4 (n=32)	35.8 (n=19)	23.3 (n=13)
	Cotton	30.2 (n=33)	28.4 (n=15)	32.1 (n=18)
RF sock	Tierra	29.4 (n=32)	35.8 (n=19)	23.3 (n=13)
	Set	40.4 (n=44)	35.8 (n=19)	44.6 (n=25)
	Cotton	30.2 (n=33)	28.4 (n=15)	32.1 (n=18)

Km=Kilometres, n=sample size, %=Percentage, ±=Standard deviation, kg=Kilogrammes, BMI=Body mass index, LF=Left foot, RF=Right foot.

4. Study variables

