None of the other dermal lesions included in the evaluation (reddened skin, urticaria, crevice and heloma) were detected. Significant differences were found between the percentage of dermal lesions in hikers wearing technical socks (6.6%) and non-technical socks (36.4%) (p-value=0.000). The women had a higher percentage of dermal lesions (23.2%) than the men (7.5%) (p-value=0.034), regardless of sock type. Moreover, the percentage of women with dermal lesions was significantly higher among wearers of non-technical socks (50%) than in wearers of technical socks (10.5% had lesion) (p-value=0.002). Particularly the women presented more blisters in both RF and LF when they wore cotton sock compared to the Tierra and Set socks (RF p-value = 0.050, LF p-value = 0.042). In the case of men, there was no difference in any of the skin lesions at 14.5 km on any foot compared to the sock used (Table 3). The most frequent muscle lesions at the end of the first part of the hike were pain due inadequate warm (21.1%), inflammation (2.8%) and muscle discomfort (1.8%). No sprains or nail disorders were detected at the end of the first part of the hike. No difference between any of muscle lesions analyzed and technical and non-technical socks were found. By sex, no differences were found regarding technical and non-technical socks or concerning the model used sock on each foot (Table 3).

Table 4. Prevalence of skin, muscle and nail lesions during the 14.5-29.6 km of the hike by sex.

(14.5-29.6 km)				Fema	ale					N	I ale		
(14.5-29.6 KM)		Tie	rra %	Set	%	Cott	on %	Tier	ra %	Se	et %	Cott	on %
Skin lesion	%Tt.	RF	LF	RF	LF	RF	LF	RF	LF	RF	LF	RF	LF
Blister	19.6	7.7	12.0	20.0	7.7	25.0	12.5	5.3	0.0	5.3	21.1	6.7	0.0
Erosion	7.5	0.0	4.0	8.0	0.0	12.5	18.8	0.0	0.0	0.0	0.0	20.0	13.3
Reddened skin	3.7	0.0	0.0	0.0	0.0	18.8	18.8	0.0	0.0	0.0	0.0	6.7	6.7
Urticaria	0.9	0.0	0.0	0.0	0.0	6.3	6.3	0.0	0.0	0.0	0.0	0.0	0.0
Crevice	0.9	0.0	0.0	0.0	0.0	0.0	0.0	0.0	0.0	0.0	0.0	6.7	0.0
Heloma	0.9	0.0	0.0	0.0	0.0	0.0	0.0	0.0	0.0	0.0	0.0	6.7	6.7
(14.5-29.6 km)			Female			Male							

		Tier	ra %	Set	t %	Cott	on %	Tier	a %	Se	et %	Cott	on %
Muscle lesion	%Tt.	RF	LF	RF	LF	RF	LF	RF	LF	RF	LF	RF	LF
Pain due inadequate warm	11.2	15.4	4.0	4.0	7.7	0.0	12.5	10.5	0.0	5.3	10.5	0.0	0.0
Inflammation	0.9	0.0	4.0	4.0	0.0	0.0	0.0	0.0	0.0	0.0	0.0	0.0	0.0
Muscle discomfort	0.9	0.0	0.0	0.0	0.0	0.0	0.0	0.0	0.0	5.3	0.0	0.0	0.0
Sprain	0.9	0.0	0.0	4.0	0.0	0.0	0.0	0.0	0.0	0.0	0.0	0.0	0.0
(14.5-29.6 km)				Fem	ale					N	Iale		

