The study of the perimeter of hikers' feet analysed in total and by gender, in relation to distance and sock type, did not reveal significant results (data not shown).

Table 7. Probability of suffering skin and muscle lesions in relation to anthropometric variables and sock type throughout the hike.

1	PROBABILITY SKI	N LESIONS	PROBABILITY M	USCLE LESIONS		
Dist	ance:	Distance: 14.5-29.6 Km	Distance: 0-14.5 Km			
96% If	female	90% If male	100% I	f male		
100% If non-	technical sock	100% If non-technical sock	67% If non-te	chnical sock		
Direct relation	Inverse relation	Inverse relation	Direct relation	Inverse relation		
BMI	Age	Age	BMI	Age		

km=Kilometre, %= Percentages, BMI=Body mass index.

It was possible to study the relation between variables and predict the probability of lesions developing during the hike using logistic regression analysis (Table 7). Women have a higher probability than men of suffering skin lesions in hikes of up to 14.5 km. However, men have a higher probability than women of suffering skin lesions on hikes of 14.5 to 29.6 km and muscle lesions on hikes of up to 14.5 km.

The non-technical socks showed the highest probability of wearers suffering dermal and muscle lesions, both from 0-14.5 km and from 14.5 km to the end of the hike. The probability of dermal and muscle lesions developing in relation to the quantitative variables showed direct and inverse relations. From 0-14.5 km, the BMI and age of hikers are directly and inversely related, respectively, both in dermal and in muscle lesions. In the second part of the hike, age continued to show an inverse relation with skin lesions, but no relation with BMI was identified (Table 7).

Supplementary data

Protocol of Measures. Top shows the protocol of measure at the starting point (0 km). Middle part includes the protocol of the first part of the hike (0-14.5 km) and lower part of the table reflex the measurement protocol of the second part of the hike (14.5-29.6 km)

PPOTOCOI	OF MEASURES
STARTING POINT (0 Km)	OF MEASURES
Dorsal Number: Gender: Gender:	Foot size Weight Size
Body mass index (BMI):	The state of the s
	Previous Alterations on skin, muscles or
nails	
	rature LF
Plantar Plantar	
Dorsal Dorsal	
Perimeters RF: (Three different measures)	Perimeters LF: (Three different measures)
tibia	tibia
hell	hell
toes instep	toes instep
FIRST PART OF THE HIKE (0-14.5 Km)	Perimeters RF: (Three different measures)
	tibia
Temperature RF: (Three different measures)	
Plantar	

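### First-part skin-lesion model: 17 events for what appear to be four predictors, so ordinary odds ratios would be expected to run roughly 10–25% high; a penalised fit with intervals is a cheap improvement

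*Combined protocol and SAP*

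**What the plan says.** Section 6 (Statistical tests) names SPSS version 22 and describes the logistic analysis in one sentence: "The variables analysed by logistic regression were quantified using the ODDS Ratio (OR"). It does not say whether the variables enter one model or several, how they are coded or selected, whether the unit is the hiker or the foot, or how the model is estimated.

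The Results then rely on the analysis: "It was possible to study the relation between variables and predict the probability of lesions developing during the hike using logistic regression analysis". For the first part of the hike, Table 7 and its text link skin lesions to four variables:
- sex: "Women have a higher probability than men of suffering skin lesions in hikes of up to 14.5 km";
- sock type: "The non-technical socks showed the highest probability of wearers suffering dermal and muscle lesions";
- BMI, with a direct relation;
- age, with an inverse relation.

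Table 7 shows 96% against female sex and 100% against the non-technical sock. No odds ratio or confidence interval appears anywhere.

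**The concern.** Ordinary maximum likelihood pushes logistic coefficients away from zero when there are few events per coefficient. The first-part skin-lesion outcome has few events, and only one of them is among the 38 men in technical socks.

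The logistic model is the only named analysis that could adjust the sock effect for age and BMI, and the Results use it for prediction. If the promised odds ratios are produced by an ordinary joint fit, a reader should expect them to be somewhat too large on average.

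**Working it through.** **Inputs.** "The sample comprised 109 participants (53 men and 56 women"). Table 1 gives 33 cotton wearers (15 men, 18 women), which leaves 76 in technical socks (38 men, 38 women). The first-part rates are in the Results:
- "hikers wearing technical socks (6.6%) and non-technical socks (36.4%) (p-value=0.000");
- "The women had a higher percentage of dermal lesions (23.2%) than the men (7.5%) (p-value=0.034");
- among women, "wearers of non-technical socks (50%) than in wearers of technical socks (10.5% had lesion) (p-value=0.002").

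**Event count.** Rate × denominator gives whole numbers.
- By sock: 0.066 × 76 = 5 and 0.364 × 33 = 12, total 17.
- By sex: 0.232 × 56 = 13 and 0.075 × 53 = 4, total 17.
- Women: 9/18 cotton and 4/38 technical. Men, by subtraction: 3/15 and 1/38.

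**Reproducing the printed p-values.** Two-sided Fisher tests on these counts give 0.0002 (printed 0.000, which section 6 defines as below 1 per 1000), 0.0337 (printed 0.034) and 0.0021 (printed 0.002). The counts are therefore secure.

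**Events per coefficient.** One joint model with four coefficients has 17/4 = 4.25. With six coefficients it has 17/6 = 2.8.

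**Fit to the documents' own counts (sock + sex only).** OR = exp(b); Wald 95% CI = exp(b ± 1.96 × SE).

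| | ML: b (SE) | OR (95% CI) | Firth: b (SE) | OR (95% CI) |
|---|---|---|---|---|
| Cotton vs technical | 2.162 (0.609) | 8.69 (2.6–28.7) | 2.063 (0.588) | 7.87 (2.5–24.9) |
| Female vs male | 1.414 (0.653) | 4.11 (1.1–14.8) | 1.311 (0.627) | 3.71 (1.1–12.7) |

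The ML-to-Firth ratios are 8.69/7.87 = 1.10 and 4.11/3.71 = 1.11. Age and BMI cannot be added, because no individual data are printed.

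**Expected inflation (simulation).** The sock-by-sex layout was kept at n = 109. In the multi-predictor runs the intercept was set for about 17 events, with 2,500–4,000 trials per scenario. Inflation = exp(mean b − true b) − 1, with separated ML fits left out of the ML mean (0.2–1.8% in the multi-predictor runs).

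Assumptions not in the documents:
- age log OR 0 to −0.6 per 10 years;
- BMI log OR 0 to +0.6 per 3.6 units;
- ages clipped to 18–80;
- female BMI SD 3.6. Using the printed 9.1 instead gives sock +25% and sex +13%.

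| Model and true ORs (sock; sex) | ML sock | ML sex |
|---|---|---|
| One predictor per model (8.1; 3.7) | +8% | +8% |
| Sock + sex (7.9; 3.7) | +11.5% | +12% |
| Four predictors (7.9–8.7; 3.7–4.1) | +20 to +26% | +13 to +20% |
| Four predictors, weaker effects (4; 2.5) | +10% | +9% |
| Six predictors (7.9; 3.7) | +32% | +22% |

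Firth's average bias in all of these is about −2% to +3%. In four-predictor runs with a true sock OR of 8.7, the RMSE of the sock log OR falls from about 0.76–0.83 (ML) to 0.63–0.69 (Firth).

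**The case against.** The strongest objection is that the criticised model is inferred. Section 6 does not specify a joint model, and Table 7 is also compatible with one model per variable, where inflation is only about 8%. SPSS and the absence of any named penalty make maximum likelihood likely, but they do not establish a joint fit. This stands, so the figure must stay conditional.

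Several stronger readings are tempting, and the documents do not support them.
- *The reported odds ratios are too large.* None is printed, so none can be called wrong. The assumed true effects also sit near the observed ones; with weaker effects the bias is nearer 10%.
- *The bias explains Table 7's 96% and 100%.* It cannot. Read as OR/(1 + OR), which is an assumption, 96% implies 0.96/0.04 = 24, and 100% (at least 99.5%) implies 0.995/0.005 = 199 or more, against 4.1 and 8.7 from the counts. Read as lesion risks, they conflict with the observed 23.2% and 36.4%.
- *The model separates.* All four sock-by-sex cells contain both events and non-events, so separation on those two factors did not occur.
- *Only this model can separate sock from sex.* The Results already compare socks within each sex. The point holds for age and BMI only.
- *The second part has the same problem.* The printed 21.1% and 54.8% fit 16/76 and 17/31, so about 33 events, or 33/4 = 8.25 per coefficient. That part was not simulated.

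It is also fair that the shift is small against the interval, and that the main sock and sex findings rest on direct comparisons that do not use this model.

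**Conclusion.** The point holds in conditional form. The 17 events are exact, and four predictors is a fair reading of Table 7. If they were fitted jointly by ordinary maximum likelihood, the sock and sex odds ratios would be expected to be inflated on average by roughly 10–25%, with about 8–32% spanning the model forms and effect sizes tried. This rests on the assumed estimator and model, and on the assumed age and BMI effects.

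A penalised fit removes nearly all of the average log-odds bias and lowers the RMSE. It does not cure imprecision: the sock interval on the Firth fit still runs from about 2.5 to 25. The sock conclusion survives. This is a worthwhile, inexpensive improvement to an under-specified analysis, not a demonstrated error in a result.

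**What to change.** In section 6, state the first-part skin-lesion model in full: hiker as the unit; sock (technical or cotton), sex, age and BMI as fixed predictors in one model; Firth penalised logistic regression. Report the odds ratios with profile-likelihood 95% intervals in place of Table 7's percentages.

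If predicted probabilities are reported, re-estimate the intercept after the penalised fit. Plain Firth over-predicts slightly: fitted events total 17.8 against 17 observed on the sock + sex counts, and about 18 against 17 in the four-predictor simulations.

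The cost is one re-fit, possibly outside SPSS 22, and somewhat smaller odds ratios. The intervals will remain wide.
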